11.1.1 Overview of AEs		
Population	:	Safety population
Contents	:	
Overview AE table will be tabulated and will present number and percentages of subjects and number of events with following items.
 
• AEs• ADRs• AEs with fatal outcome• SAEs• AEs leading to premature discontinuation from the study• Events of special interest

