10.2.2 Figures of Lung Density Versus Time Curves of Individual Subjects (GTI1401-OLE only)	
Population	: Safety population
Contents	: For individual subject, Hu value 15 percentile [g/L] versus time plot will be presented using “Lung” as a target location in one figure using analysis visit (Annually) plotted on the x-axis.

10.2.3 Figures of Mean value of Lung Density Versus Time Curves of All Subjects (GTI1401-OLE only)	
Population	: Safety population
Contents	: Follow the same procedure as Figure 10.2.2 except plot mean Hu value 15 percentile [g/L] versus time plot using all subjects.

Table: Lung Density Parameter

Contents	Conversion formula for analysis value	Digits to be displayed
Hu value 15 percentile [g/L]	Original value [housfield unit] + 1000	1 decimal place
Mean [g/L]	Original value [housfield unit] + 1000	1 decimal place
Standard deviation [g/L]	Original value [g/L]	1 decimal place
Percent below -856 hu [%]	Original value	1 decimal place
Percent below -910 hu [%]	Original value	1 decimal place
Percent below -950 hu [%]	Original value	1 decimal place
Total volume in cm3 [mL]	Original value	1 decimal place
Air volume in cm3 [mL]	Original value	1 decimal place
Tissue volume in cm3 [mL]	Original value	1 decimal place

Table: Target Location

1	:	Lung
2	:	Lung, Left
3	:	Lung, Left Lower Lobe
4	:	Lung, Left Upper Lobe
5	:	Lung, Right
6	:	Lung, Right Lower Lobe
7	:	Lung, Right Middle Lobe
8	:	Lung, Right Upper Lobe
9	:	Lung, Thirds Left Lower
10	:	Lung, Thirds Left Middle
11	:	Lung, Thirds Left Upper
12	:	Lung, Thirds Right Lower
13	:	Lung, Thirds Right Middle
14	:	Lung, Thirds Right Upper

11 Safety Analysis

Adverse Events

Definition of Adverse Events

Adverse Event:	
An AE is any untoward medical occurrence in a subject or clinical investigation subject administered a pharmaceutical product, which does not necessarily have a causal relationship with this treatment.
 
An AE can therefore be any unfavorable and unintended sign (including an abnormal laboratory finding), symptom, or disease temporally associated with the use of a medicinal product, whether or not considered related to the IMP.
 
In this protocol, non-serious COPD exacerbation will not be considered as adverse events unless SAE.

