TEAE for GTI 1401	
Treatment emergent adverse events (TEAE) for GTI 1401 will be defined as any adverse event occurred after or on the first study drug infusion of GTI 1401 to the final visit of GTI 1401.
 
For any subject, all AEs that occur at any time from the beginning of Alpha-1 MP administration until the final visit of the clinical trial will be considered as TEAE.
 
All tables regarding to Adverse Events are restricted to TEAE.

TEAE for GTI1401-OLE	
Treatment emergent adverse events (TEAE) for GTI 1401-OLE will be defined as any adverse event occurred after or on the first study drug infusion of GTI 1401-OLE to the final visit of GTI 1401-OLE or adverse event which continue from GTI 1401 to GTI 1401-OLE.
 
For any subject, all AEs that occur at any time from the beginning of Alpha-1 MP administration until the final visit of the clinical trial will be considered as TEAEs
 
All tables regarding to Adverse Events are restricted to TEAE.

Adverse Drug Reaction (ADR):	The phrase “responses to a medicinal product” means that a causal relationship between a medicinal product or study treatment and an AE is at least a reasonable possibility, that is, the relationship cannot be ruled out.

	
When an AE is classified, assessing causal relationship by the Investigator, as “definitive”, “probable”, “possible” or “doubtful/unlikely”, the event will be defined as a suspected ADR. When the causal relationship is labeled “Unrelated”, then it will be considered that the AE is not imputable to the study treatment and it is not a suspected ADR.

Serious Adverse Events (SAEs):	
Any event reported on the AE CRF form with the serious field ticked “Yes”.
 
A SAE is any untoward medical occurrence that at any dose:
 
Results in deathIs life-threatening 
Note: The term “life-threatening” in this definition refers to an event in which the subject is at risk of death at the time of the event; it does not refer to an event that hypothetically might cause death if it were more severe.
 
Requires inpatient hospitalization or prolongation of existing hospitalization
 
Results in persistent or significant disability/incapacity
 
Is a congenital anomaly/birth defect

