Events of Special Interest:	
Events of special interest include the following:
 
All COPD exacerbations occurring during the study will be recorded. Each subject will be assessed for signs and symptoms of exacerbations at each study visit as specified in Appendix 1 and Appendix 2. Given that COPD exacerbations are part of the natural history of AATD, COPD exacerbations will not be reported as AEs unless a COPD exacerbation meets the criteria of a SAE. If an exacerbation meets criteria for a SAE, it will be reported as such, and the standard of care should be followed. Results from standard of care should be obtained and reported.

Adverse events with incomplete start dates will be considered treatment emergent (TEAE) if:

- Day and Month are missing and the year is equal to or after the year of the first study drug dose date of each study (1401/1401-OLE);
- Day is missing, month is present and the month is equal or after the month of first dose of each study (1401/1401-OLE) and the year is equal or after the year of first dose date of each study (1401/1401-OLE);
- Day is missing and the year is equal to the year of the first infusion date of each study (1401/1401-OLE) and the month is equal to or after the month of the first infusion date of each study (1401/1401-OLE);
- Complete date is missing.

The AE tables will include the number and percentage of subjects by MedDRA primary System Organ Classes (SOC) - sorted by alphabetical order, MedDRA Preferred Terms (PT) - sorted by alphabetical order. A subject with more than one occurrence of the same adverse event in a particular system organ class/preferred term will be counted only once in the total of those experiencing adverse events in that particular system organ class/preferred term.

If a subject experiences the same adverse event at more than one severity, or with more than one relationship to study drug, the most severe rating or the stronger causal relationship to study drug will be given precedence. Any missing severity/relationship will be accounted as “worst case” as related in the tables.

All AE tables will be provided without separating AE occurred during treatment period with Follow-up period.

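### SAP 11.1.1: applied literally, the AE-table rules leave only serious COPD exacerbations in the special-interest row, although that category is defined by all exacerbations (minor)

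*SAP*

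**What the plan says.** The definitions at the start of SAP Section 11 and the table specification in 11.1.1 contain five statements that bear on this row.

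- **AE definition:** "In this protocol, non-serious COPD exacerbation will not be considered as adverse events unless SAE".
- **TEAE definition for GTI1401:** "any adverse event occurred after or on the first study drug infusion of GTI 1401 to the final visit of GTI 1401". The definition for GTI1401-OLE likewise starts from an adverse event.
- **Table restriction, stated for each study:** "All tables regarding to Adverse Events are restricted to TEAE".
- **Events of special interest:** the entry has one item, COPD exacerbations. It says "All COPD exacerbations occurring during the study will be recorded" and "Each subject will be assessed for signs and symptoms of exacerbations at each study visit as specified in Appendix 1 and Appendix 2", and then "COPD exacerbations will not be reported as AEs unless a COPD exacerbation meets the criteria of a SAE".
- **Table 11.1.1, Overview of AEs:** "Overview AE table will be tabulated and will present number and percentages of subjects and number of events with following items". Its six rows are AEs, ADRs, fatal AEs, SAEs, AEs leading to discontinuation, and events of special interest.

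The list of AE listings after 11.1.6 includes one for non-serious COPD exacerbations. Its title calls them AEs. Section 4.2 names COPD exacerbations as a study variable separate from adverse events.

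**The concern.** The definition of the category and the rule for filling AE tables give different contents for the same row. Two programmers could each follow the SAP and report different counts, one by flagging exacerbations among the TEAE records and the other by counting every exacerbation recorded.

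Safety is the primary objective of both studies (Section 3.1), and this row is the only summary output in the safety section that could hold COPD exacerbations as a category. Under the literal rules it would show zero if every exacerbation were non-serious, even though events of special interest had occurred. A reader of the overview table would have no sign of this.

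**Working it through.** The SAP states no figure to reproduce, so the check sets its rules side by side.

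**What the rules put in the row**

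1. By the AE definition and the special-interest entry, a non-serious exacerbation is not an AE.
2. By the TEAE definitions, every TEAE is an AE. A non-serious exacerbation is therefore not a TEAE.
3. By the table restriction, AE tables hold TEAEs only. It applies to whole tables and names no exception.
4. Table 11.1.1 is titled and described as an AE table, so the restriction covers it.
5. The special-interest row therefore holds only serious treatment-emergent exacerbations. Each of these is also an SAE, so the row is a subset of the SAE row in the same table.

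**What the category definition puts in the row**

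The special-interest entry covers all COPD exacerbations and does not limit them by seriousness.

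**Difference**

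Within the treatment-emergent window, let *s* be the number of serious exacerbations, *n* the number of non-serious ones, and *k* the number of subjects whose exacerbations were all non-serious.

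- Events, literal rules: *s*
- Events, category definition: *s* + *n*
- Difference in events: (*s* + *n*) − *s* = *n*
- Difference in subjects: *k*

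The SAP gives no exacerbation rate, so neither *n* nor *k* can be estimated. If *n* = 0, the two readings agree.

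**Whether another table in Section 11 recovers the events**

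| Subsection | Tables | Content |
|---|---|---|
| 11.1 | 6 | AE overview; AEs and ADRs |
| 11.2 | 3 | Laboratory tests |
| 11.3 | 1 | Vital signs |
| 11.4 | 1 | ECG |
| 11.5 | 1 | Urine cotinine |
| 11.6 | 2 | Lung function |

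The total is 6 + 3 + 1 + 1 + 1 + 2 = 14. Apart from 11.1.1, that leaves 14 − 1 = 13 tables. Tables 11.1.2 to 11.1.6 take AEs or ADRs, and those in 11.2 to 11.6 take other measurements. None has a place for a non-serious exacerbation, so the listing is the only output that shows one.

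**The case against.** The strongest reply is that a workable reading already exists. The row is labelled as events rather than AEs, and it has its own definition beside those of AE, TEAE, ADR and SAE. A specific definition would normally govern the row that bears its name. The restriction to TEAEs follows a definition about timing, so it can be read as a device to keep out pre-treatment events. The listing also shows that the SAP handles non-serious exacerbations among its AE outputs. A row that merely repeats part of the SAE row is unlikely to be what the authors wanted.

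This stands as an account of intent, and it is why the point is minor. It does not remove the conflict. The restriction is written without exception, the TEAE definition concerns AE status as well as timing, and no sentence releases this row from either. The listing shows the events by subject but does not settle the counts that 11.1.1 asks for.

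Three stronger readings are tempting, and the SAP does not support them.

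- **A large numerical effect.** With a target of at least 3 subjects (Section 5.4), a reader might take one subject's share of the percentage as the size of the problem. That share only shows how coarse percentages are at such a size. Without an event rate it says nothing about the expected error, and at that size the listing lets a reader count the events directly.
- **A carry-over rule for exacerbations.** The OLE definition of a TEAE adds "or adverse event which continue from GTI 1401 to GTI 1401-OLE". That clause concerns AEs, and the SAP states no such rule for exacerbations.
- **Certainty about the data.** A reader might infer from the appendices that everything needed is already collected. They show that exacerbations are assessed, but not which fields are recorded or where the records are held.

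**Conclusion.** The point holds as a minor error of wording. The SAP's rules for AE tables contradict its own definition of events of special interest. Followed exactly, they exclude non-serious exacerbations from the only summary row meant for that category.

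The effect is confined to one descriptive row in the overview table of each study. Its size is the number of non-serious treatment-emergent exacerbations, which the SAP gives no means of predicting. No test or decision rule depends on the row, and the listing keeps the events visible.

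The conclusion rests on applying the restriction as written. The intent was probably to count all exacerbations. Not reporting non-serious exacerbations as AEs is a reporting convention that this point does not dispute.

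**What to change.** In 11.1.1, state that the special-interest row counts all COPD exacerbations, serious and non-serious, recorded on or after the first infusion of each study and up to its final visit. State also that this row is exempt from the requirement that an event be an AE. Leave the AE-reporting convention in Section 11 unchanged.

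The cost is one or two sentences of SAP wording and the matching line in the specification of one table. No other table in Section 11 changes.

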3.1 Primary Objectives

The primary objective of GTI1401 study is to evaluate the safety of 60 mg/kg Alpha-1 MP administered by weekly IV infusions over eight weeks in Japanese subjects with AATD.

The primary objective of GTI1401-OLE study is to evaluate the long-term safety of 60 mg/kg Alpha-1 MP administered by weekly IV infusions for approximately one year or longer (can be renewed annually with the consent of the subjects) in adult subjects with AATD in Japan.

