- Immediately after infusion completion (after sodium chloride [NaCl] flush) (0 hour)
- 15 minutes after infusion completion
- 2 hours after infusion completion
- 4 hours after infusion completion
- 8 hours after infusion completion
- 24±4 hours (1 day after infusion completion)
- 48±4 hours (2 days after infusion completion)
- 120 hours ± 1 day (5 days after infusion completion)
- 168 hours ± 1 day (7 days after infusion completion) (Week 9 Visit)

At the Week 9 visit, subjects have the option to participate in an open-label extension (OLE) study (GTI1401-OLE) in which subjects, if they opt to enroll, will continue to receive 60 mg/kg Alpha-1 MP for at least another year (with the optional subsequent annual extensions) to assess the long-term safety of Alpha-1 MP. Week 9 of the GTI1401 study is also the first week of the extension study (GTI1401-OLE). If subjects do not opt to participate in Study GTI1401-OLE, they will come back to the clinic 30 days (4 weeks) after the last Alpha-1 MP infusion for the Follow-Up/End of Study Visit (Week 12).

A schematic of the overall study design is shown in Figure 1 below. The schedule of events for GTI1401 and GTI1401-OLE studies can be found in appendix 1 and appendix 2.

- Final Visit/Early Termination = Follow-up/Final Evaluation Visit. Subjects who discontinue early from the study will need to complete this study visit 30days (≈ Weeks) after the last study drug infusion.
- At the Week 9 visit, subjects will be given the option to participate in the GTI1401-OLE. If they are enrolled in Study GTI1401-OLE, the Week 9 visit will be their End of Study Visit of GTI1401 study.

Figure 1 Overall Study Schema

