5.7 Denominator

Unless otherwise mentioned, denominator of percentage in each table will be the number of population designated in each table.

6 Subject Disposition Subject Disposition

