9.3 Treatment Compliance

Treatment compliance will be calculated as:

$$\frac{\text{TotalVolumeInfused}}{\text{TotalVolume Prepared}} \times 100\%$$

The total volume prepared is collected on the eCRF and is calculated based on the subject's weight at baseline.

The total volume prepared and dispensed by pharmacist is the intended dose volume a subject should be given based on the body weight.

Infusion compliance will be calculated as:

$$\frac{\text{The Number of Actual Infusions}}{\text{The Number of Infusions Expected}} \times 100\%$$

For subjects who drop out from the study early, the number of infusions expected will depend on the number of weeks the subjects are in the study.

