11.1.2 Summary Table of AEs
11.1.3 Summary Table of ADRs
Population
Contents

Population : Safety population

Contents : The number and percentage of incidences of AEs and ADRs in separate table by SOC and PT

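### The OLE adverse-event tables give only crude percentages and event counts, which mix event frequency with length of follow-up; the overview table should add a rate per patient-year

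*SAP*

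**What the plan says.** **Objective and follow-up.** SAP section 3.1 makes long-term safety the primary objective of GTI1401-OLE, over about a year or longer, and adds that treatment "can be renewed annually with the consent of the subjects". Section 4.1 says that subjects who enrol continue "for at least another year (with the optional subsequent annual extensions) to assess the long-term safety of Alpha-1 MP". The OLE definition of a treatment-emergent event (section 11) runs from the first OLE infusion to the final OLE visit with no upper limit. It also takes in events that continue from GTI1401.

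**AE metrics.** The overview in 11.1.1: "Overview AE table will be tabulated and will present number and percentages of subjects and number of events with following items". The general text of section 11: "The AE tables will include the number and percentage of subjects by MedDRA primary System Organ Classes (SOC" and by preferred term, with each subject counted once per term. For 11.1.2 and 11.1.3: "The number and percentage of incidences of AEs and ADRs in separate table by SOC and PT". The causality and severity tables (11.1.4 to 11.1.6) follow the same pattern. Under section 5.7, unless otherwise mentioned, the "denominator of percentage in each table will be the number of population designated in each table", that is, a number of subjects.

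**Exposure.** Section 9.2.1 derives treatment duration and number of infusions, but in a table of its own that no AE output draws on. Section 9.3 does allow for unequal time in the study, for infusion compliance only: for subjects who leave early, "the number of infusions expected will depend on the number of weeks the subjects are in the study".

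**The concern.** The same crude metrics serve an 8-week study and an extension with no fixed end. Even if the underlying event rate is constant, the percentage of subjects with at least one event climbs towards 100% as follow-up lengthens, and event counts grow in proportion to time. Section 5 presents the two studies separately but with identical metrics. A reader who sets the OLE tables beside the GTI1401 tables would see an apparent increase that time alone can produce.

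What is at stake is how the results for the OLE's primary objective can be read. COPD exacerbations, the event of special interest, can recur and are described in section 11 as part of the natural history of the disease. A rate is particularly useful for them.

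**Working it through.** The SAP states no event rate, so there is no figure of its own to reproduce. The event rates and follow-up times below are assumptions, shown over a range.

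**Step 1. Effect of follow-up on the percentage of subjects.** With a constant rate r per patient-year and follow-up T in years, the expected share with at least one event is 1 − exp(−rT). Eight weeks is T = 8/52 = 0.154. For example, r = 0.5 and T = 1 gives 1 − exp(−0.5) = 39.3%.

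| Assumed r per year | 8 weeks | 1 year | 2 years | 4 years |
|---|---|---|---|---|
| 0.1 | 1.5% | 9.5% | 18.1% | 33.0% |
| 0.5 | 7.4% | 39.3% | 63.2% | 86.5% |
| 1 | 14.3% | 63.2% | 86.5% | 98.2% |
| 2 | 26.5% | 86.5% | 98.2% | 100.0% |

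Within each row the rate is the same throughout.

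**Step 2. Three subjects (the minimum in section 5.4), r = 0.5.** Expected percentage = mean of 1 − exp(−rTᵢ); expected events = r × ΣTᵢ; rate = events / ΣTᵢ.

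| Follow-up in years | Expected % of subjects | Expected events | Events per patient-year |
|---|---|---|---|
| 1, 1, 1 | 39.3% | 0.5 × 3 = 1.5 | 1.5/3 = 0.50 |
| 1, 2, 4 | (39.3 + 63.2 + 86.5)/3 = 63.0% | 0.5 × 7 = 3.5 | 3.5/7 = 0.50 |
| 4, 4, 4 | 86.5% | 0.5 × 12 = 6.0 | 6.0/12 = 0.50 |

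Both planned measures move with follow-up; the rate does not.

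**Step 3. Does the 9.2.1 duration suit as denominator?** The formula is (last dose date − first dose date + 7)/7 weeks. Eight weekly infusions give (49 + 7)/7 = 8.0 weeks, or 56 days. Section 11 pools the treatment and follow-up periods in the AE tables. A GTI1401 subject who does not enter the OLE is seen 30 days after the last dose (section 5.3.4), so events are captured for 49 + 30 = 79 days. Dividing by 56 days would inflate that subject's rate by 79/56 = 1.41, about 40%. A subject who enters the OLE ends GTI1401 at Week 9, day 56, where the two agree. For 52 weekly OLE infusions the formula gives (357 + 7)/7 = 52.0 weeks, which agrees with the Ext Week 53 call in Appendix 2 (52 weeks after Ext Week 1). The mismatch would therefore fall on the GTI1401 rate and could create a spurious decline into the OLE.

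**Step 4. Precision (exact Poisson 95% intervals).**
- 1 event in 3 × 8/52 = 0.46 patient-years: 2.2 per year (about 0.05 to 12).
- 2 events in 3 patient-years: 0.67 (0.08 to 2.41).
- 4 events in 7 patient-years: 0.57 (0.16 to 1.46).

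**The case against.** **The crude figures are legitimate.** In a single-arm, descriptive study with no formal sample size, numbers and percentages of subjects plus event counts describe correctly what was observed. This stands. A reader might infer that the planned figures measure exposure instead of risk and are therefore wrong; the documents do not support that. The figures reflect both, and they should stay in the tables.

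**Unequal follow-up is not stated.** A reader might also take it as given that follow-up differs by subject. The SAP does not say so. It is a fair inference from annual renewal by consent and from the provision for early drop-out, and the schedule in Appendix 2 runs only to Ext Week 53. Even with equal OLE follow-up, however, 8 weeks and a year or more remain incomparable on these metrics.

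**An overall rate can be worked out by hand.** The overview gives event counts, 9.2.1 gives mean duration and number of subjects, and AEs are listed by subject. This largely stands and limits the harm. But the simple division would use a duration that may not match the capture window, and an OLE count that includes carried-over events. Fixing the calculation in advance avoids choosing numerator and denominator after the fact.

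**The sample is too small for rates to show anything.** This stands for trends: the intervals in step 4 are too wide to tell whether event frequency rises, falls or stays level after the first 8 weeks. The SAP sets no such comparison as an objective either. It does not make a descriptive rate useless, because the crude percentages rest on the same few subjects and also depend on time.

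**Conclusion.** The point holds as a worthwhile, inexpensive improvement and not as an error that invalidates the analysis. For a primary objective of long-term safety with open-ended follow-up, the AE tables fix a metric that mixes event frequency with length of observation. At a constant assumed rate of 0.5 per patient-year, the expected percentage moves from 39.3% to 86.5% between 1 and 4 years. Over assumed rates of 0.1 to 2 the shift runs from 9.5% to 33.0% at one end and from 86.5% to 100.0% at the other. Expected event counts rise fourfold in every case.

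These sizes rest on assumed constant rates and assumed follow-up of up to 4 years, neither of which the SAP gives. They are expectations: with 3 subjects an observed percentage can only be 0, 33, 67 or 100. It would go too far to say that adding rates would reveal a change in risk since GTI1401; the numbers are too small for that.

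**What to change.** In the 11.1.1 overview table, for each study, keep the crude figures and add total person-time and events per patient-year for AEs, ADRs, SAEs and COPD exacerbations. Specify:

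- **Denominator:** time from the first infusion in that study to that study's final visit, matching the AE capture window, and not the 9.2.1 treatment duration. Alternatively, keep the 9.2.1 duration and restrict the numerator to events within that window.
- **OLE numerator:** only events with onset in the OLE; those continuing from GTI1401 stay in the crude tables but are left out of the rate.
- **Label:** descriptive, with no inference about a trend between the two studies.

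The SOC and preferred-term tables need not change. They count each subject once per term, so a rate there would need a different counting unit.

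The cost is two columns in one table and one derived person-time variable from dates already needed for the AE window. The downside is that, with about 3 subjects, the rates will be very imprecise and could be over-read if not labelled.
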